8.3 Endpoint

8.3.1 Primary Endpoint

Subject implantation rate is defined as number of intrauterine gestational sacs divided by the number of embryos transferred, as assessed at PET Days 21 to 28.

8.3.2 Secondary Endpoints

- Subject pregnancy result (positive/negative) at PET Day 14
- Subject with confirmed ongoing pregnancy (yes/no) at PET Days 70 to 84
- Device incidents

Substance Code Clinical Performance and Safety Investigation of ENDOmetrial Washing
MEdical DEvice Forielle
Protocol Number MS 700623_0009

8.4 Analysis Sets

Intent-to-Treat (ITT) set: The ITT set will include all randomised subjects. In this population, procedure (Forielle /Control) will be assigned based upon the procedure arm to which subjects were randomised regardless of which procedure they actually received.

Per Protocol set (PP): The PP set will include all subjects who do not have major protocol violations that would affect the evaluation of the primary clinical performance endpoint.

Protocol deviations categories with severity will be described in statistical analysis plan document. Before interim/final analysis, all reported protocol deviations will be reviewed and evaluated for any impact on primary endpoint analysis.

Safety set (SAF): The SAF population will include all randomised subjects on whom the intrauterine washing procedure was attempted (even if not completed). In this population, procedure (Forielle/Control) will be assigned based upon the procedure subjects actually received, regardless of the procedure arm to which they were randomised.

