4.2 Secondary Objectives

The secondary objectives of the study are to:

- Determine the Pregnancy Rate at PET Day 14
- Determine the Ongoing Pregnancy Rate during PET Days 70 to 84
- Assess the safety of Forielle by report of device incidents

Substance Code Clinical Performance and Safety Investigation of ENDOmetrial Washing
MEdical DEvice Forielle
Protocol Number MS 700623_0009

5 Investigational Plan

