6.3 Assignment to Treatment Groups

Subjects will be randomised in a 1:1 ratio to receive endometrial washing with Forielle or no endometrial washing (control group); randomised subjects will be stratified by age (< 32 years of age; 32 to 37 years of age; 38 to 41 years of age) and number of follicles >16 mm (5 to 9 follicles >16 mm; 10 to 14 follicles >16 mm). Although the subject and the investigator and site staff will be aware of the endometrial washing condition, the embryology lab will be blinded to the randomisation procedure and will not know the endometrial washing condition.

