7.1.3 Oocyte Retrieval Visit (Day 2 Post Randomization)

Subjects will return to the site approximately 34-36 hours after HCG triggering for oocyte retrieval and, when applicable based on randomisation, endometrial washing with Foriella for the Day 2 Post Randomisation (PR) visit. The following assessments and procedures will occur at the Oocyte Retrieval Visit (Day 2 PR):

- Oocyte retrieval (based on standard of care practices)
- Subjects randomised to Foriella will undergo endometrial washing per the Foriella IFU
- Provide luteal support/endometrial preparation (with 100 mg of intramuscular progesterone)
- Record adverse events, device incidents and concomitant medications
- Embryology lab will perform ICSI on oocytes retrieved
- Approximately 24 hours after ICSI, the embryology lab will perform daily embryo culture assessments to determine the embryo vitality and fertilization rate.
- The Embryology lab with the Doctor will determine how many embryos will be transferred and at which stage (e.g., either Day 5 PR or Day 7 PR), based on standard laboratory and clinical parameters. Definition of Embryo Transfer Visit should occur at this time point

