7.4 Assessment of Safety

Safety of Forielle will be assessed through the recording and reporting of medical device incidents.

In addition, any Adverse Event (AE) or Serious Adverse Event (SAE) related to the conduct of the study that would occur in a subject participating in the clinical trial will be recorded and reported through AE CRF. The analysis of these AEs/SAEs should be used to update the Forielle Risk Assessment as well as Instruction For Use.

Of note, given the design of this study and the reporting period for safety surveillance, assessment of serious adverse device effects in offspring of subjects participating in the clinical trial is not applicable (see Section 7.4.1).

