8.2 Randomisation

Eligible subjects will be randomised to receive either the intervention (Forielle endometrial washing) or no endometrial washing following oocyte retrieval on Study Day 0, the HCG Triggering day, in a 1:1 ratio.

At the HCG triggering day, on study day 0 all eligible women subjects will be randomised in ratio of 1:1 to one of two parallel treatment groups:

- Forielle
- Control (No endometrial washing)

Women subjects will be stratified with respect two factors:

- Age (age <32; 32 ≤ age <38; 38 ≤ age ≤ 41)
- n° of follicles (>16mm) (5 ≤ n° follicles ≤ 9; 10 ≤ n° follicles ≤ 14)

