8.5.4 Analysis of Safety and Other Endpoints

Device incidents will be summarized using frequency and percentages for two treatment groups.

Clinical laboratory assessments (E₂ and P₄, etc.) will be presented in listings appropriately.

Substance Code Clinical Performance and Safety Investigation of ENDOmetrial Washing
MEdical DEvice Forielle
Protocol Number MS 700623_0009

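### The Safety set in 8.4 admits only women on whom the wash was attempted, so the Control group it goes on to define contains no unwashed woman

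*Combined protocol and SAP*

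**What the plan says.** Section 8.4 sets the entry rule for the Safety set: "The SAF population will include all randomised subjects on whom the intrauterine washing procedure was attempted (even if not completed". It then says how members are grouped: "procedure (Forielle/Control) will be assigned based upon the procedure subjects actually received", whatever the randomised arm.

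The comparator is untreated. Section 8.2 lists it as "Control (No endometrial washing", and section 6.3 agrees: "Subjects will be randomised in a 1:1 ratio to receive endometrial washing with Forielle or no endometrial washing (control group". At the retrieval visit, section 7.1.3 schedules the wash for one arm only: "Subjects randomised to Foriella will undergo endometrial washing per the Foriella IFU". No sham or placebo wash is described anywhere.

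On safety, the objective in section 4.2 is "Assess the safety of Forielle by report of device incidents". The planned summary in section 8.5.4, repeated in the synopsis, is "Device incidents will be summarized using frequency and percentages for two treatment groups". It names no analysis set. Section 8.5.1 takes percentages from the size of the relevant analysis population unless stated otherwise. It also promises subject-level listings of all data and leaves table details to a separate SAP, which is not among the documents.

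Section 7.4 has study-related AEs and SAEs recorded for any participant, so in both arms, and gives them a purpose: "The analysis of these AEs/SAEs should be used to update the Forielle Risk Assessment as well as Instruction For Use".

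**The concern.** The entry rule is an exposure rule: a woman enters by having had a wash attempted. The grouping rule that follows presupposes that some members are controls. In a trial with an untreated, unshammed comparator, the first rule leaves the second with nobody to label as Control.

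What is at stake is narrow. Both arms go through ovarian stimulation, oocyte retrieval and embryo transfer, and these procedures can produce adverse events without any wash. Events in washed women are best read against that background. The control arm supplies the background and its events are collected, but the only population defined for safety leaves those women out. A SAP that carried the 8.4 definition over unchanged would produce AE tables with no comparator, although section 7.4 wants the AE analysis to inform the device's risk assessment and instructions for use.

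**Working it through.** **Inputs.** 916 women per arm, 15% drop-out, 2,156 randomised, 1:1 allocation (section 8.1); the Safety set rule and grouping rule (8.4); control receives no wash (6.3, 8.2); wash scheduled for the Forielle arm only (7.1.3); percentages based on the analysis population (8.5.1).

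**1. The plan's own total.** 2 × 916 = 1,832. 1,832 / (1 − 0.15) = 2,155.3, rounded up to 2,156. This matches the stated figure and is not in dispute. At 1:1, 2,156 / 2 = 1,078 per arm.

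**2. Apply the two rules in 8.4.** Safety set = randomised AND wash attempted. The possible cases are:

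| Randomised to | At retrieval | In Safety set? | Group by procedure received |
|---|---|---|---|
| Forielle | wash attempted | yes | Forielle |
| Forielle | no attempt | no | none |
| Control | no wash | no | none |
| Control | washed in error | yes | Forielle |

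No row puts an unwashed woman in the set. The only route in for a woman from the control arm is a wash done by mistake, and the grouping rule then counts her as Forielle.

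**3. Size of the set.** Forielle: at most 1,078, plus any control washed in error. Unwashed controls: 0 of 1,078. Share of randomised women outside the set because they are controls: 1,078 / 2,156 = 50.0%. Drop-out does not alter this, since a control fails the rule whether or not she completes the study.

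**4. Carry it to 8.5.4.** If the two-group summary uses the Safety set, the control percentage is events / 0, which is undefined. If it uses the ITT set, the denominator is about 1,078 and the percentage can be calculated. The text does not say which set is meant.

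**5. With the set defined by oocyte retrieval.** Up to 1,078 women per group and 2,156 in total, less those who never reach retrieval. The documents give no count of women lost between randomisation and retrieval, so these are upper limits.

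**The case against.** The strongest reply is that little depends on this. Section 7.4.3.2 asks about incidents associated with use of Forielle, and such incidents can arise only where the device is used. For the declared safety endpoint, women with an attempted wash are a sensible denominator, and the Control column is merely redundant. This stands: the loss for device incidents is nil.

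Second, a reader might infer that 8.4 and 8.5.4 flatly contradict each other. The documents do not support that. Section 8.5.4 names no set, and the ITT set holds both arms, so a two-group summary is possible as written. The link to the Safety set rests on its being the only population defined for safety. Even within 8.4, a labelling rule with an empty group is defective drafting rather than a logical impossibility. The emptiness itself follows from the text and does not depend on 8.5.4.

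Third, a reader might suppose that Control means women whose wash was attempted but not finished, taking received to mean completed. Nothing in the text says so, and such women would not be an untreated comparator in any case.

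Fourth, 8.5.4 plans no AE comparison between arms, so the set definition does not remove a planned table. This too stands. It would also be wrong to infer that control-arm events are lost or that no AE table is intended: AEs are recorded for all participants, SAE follow-up does not depend on the set, listings cover all data, and the separate SAP may add tables. A listing, however, is not a grouped summary, and 8.4 states the Safety set definition outright without leaving it to the SAP.

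Finally, the 50.0% only restates the allocation ratio. It describes who is left out and does not measure harm.

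**Conclusion.** The point holds as a drafting defect with a limited consequence. As written, the only defined safety population contains no unwashed control, about 1,078 of 2,156 women, and its Control group is empty. This rests on the plain wording of 8.4 and on the absence of any sham; no other section widens the set.

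Nothing changes for device incidents, the primary analysis, alpha, power or sample size. What is lost is a grouped concurrent control for study-related AEs and SAEs, and only if the Safety set is the population used for safety tables and the separate SAP does not redefine it. Reading the washing procedure in 8.4 as whichever procedure was assigned would remove the problem, but the text does not say that, and controls have no procedure to attempt. Importance is minor to moderate.

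**What to change.** In 8.4, define the Safety set as all randomised women who underwent oocyte retrieval, grouped by procedure actually received: wash attempted (even if not completed) or wash not attempted. Retrieval takes place in both arms, so it gives a common entry point and keeps the as-treated intent.

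In 8.5.4, name the Safety set as the analysis set, keep the device-incident summary, and add descriptive counts and percentages of AEs and SAEs by group. Show events before retrieval separately, including those in randomised women who never reach it, because AE recording begins at the start of stimulation and such events cannot be due to the wash. Align the synopsis and the separate SAP with this wording.

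The cost is a few sentences and a few tables from the existing AE form, with no new data. The downside is that the comparison remains descriptive. Section 7.4.2 records only events judged related to the conduct of the study, and section 6.10 leaves investigators aware of allocation, so a difference between groups could reflect differential attribution rather than the wash. The tables should say so.

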8.5 Description of Statistical Analyses

8.5.1 General Considerations

The study data will be reported using summary tables, figures, and data listings. Continuous variables will be summarized using mean, standard deviation (SD), coefficient of variation (CV%, as appropriate), median, minimum, maximum, and, as appropriate, geometric mean.

Descriptive statistics will be presented for key outcome measures. Categorical data will be summarized with the number of non-missing values and the numbers of values equal to each of the possible values. Percentages of subjects with each of the possible values will be calculated from the number of subjects in the corresponding analysis population, unless stated otherwise.

Unless otherwise specified, all formal statistical tests will be two-sided at the 5% significance level. Point estimates of treatment differences will be accompanied with two-sided 95% confidence intervals (CIs) where applicable. P-value will be used to draw statistical significant conclusions only for primary endpoint and for secondary endpoints all statistical estimates will be used for descriptive comparison.

In the case of normality assumption violations, appropriate non-parametric methods will be used for analysis.

All data will be presented in by-subject listings.

The statistical analysis will be performed using SAS[®] Version 9.2 or higher.

Substance Code Clinical Performance and Safety Investigation of ENDOmetrial Washing
MEdical DEvice Forielle
Protocol Number MS 700623_0009

All details regarding the statistical analysis and the preparation of tables, listings and figures will be described in a separate Statistical Analysis Plan (SAP) document developed by separately for interim and final analysis.

Study final analysis will be performed by PPD and Interim analysis will be performed by a PPD independent statistician from a different geographical region. A firewall will be implemented to ensure interim results will not be accessible to any PPD staff except to the independent statistician who will perform interim analysis.

8.5.2 Analysis of Primary Endpoints

The primary endpoint subject implantation rate is defined as number of intrauterine gestational sacs divided by the number of embryos transferred, as assessed at PET Days 21 to 28.

Mean subject implantation rate as assessed at PET Days 21-28 in subjects treated with Forielle endometrial washing procedure will be compared to the mean subject implantation rate in subjects who receive no endometrial washing (control group) following COS.

For the primary endpoint analysis addition to summary statistics, differences in mean subject implantation rate between study procedure and control procedure will be investigated and compared using Gamma/log normal regression model. The analysis model will include treatment procedure as the fixed effect and Embryo Transfer Day (Day 5 PR or Day 7 PR), age, number of follicles at baseline and number of embryos transferred per subject as covariates.

To evaluate the treatment comparison, estimated mean differences will be presented together with two-sided 95% confidence intervals and p-values. Appropriate distribution will be decided based on good ness of fit (residual sum of squares) value.

This primary endpoint analysis will be tested by planned group sequential design with O'Brien-Fleming type spending function. The study for clinical performance will be stopped at significance level of 0.003 in first (50% of subjects) interim analysis and at significance level 0.049 in final analysis.

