As appropriate, variables will be summarized descriptively (frequency and percentage will be summarized for categorical variables; mean, standard deviation [SD], median, and maximum will be presented for continuous variables) by study visit and by treatment group. All study data will be listed by subject. A detailed Statistical Analysis Plan (SAP) including dictionaries used for coding and software used will be prepared separately for interim and final analysis. Study final analysis will be performed by PPD and Interim analysis will be performed by a PPD independent statistician from a different geographical region. A firewall will be implemented to ensure interim results will not be accessible to any PPD staff except to the independent statistician who will perform interim analysis.

Forielle Clinical Performance

The primary endpoint, subject implantation rate, is defined as number of intrauterine gestational sacs divided by the number of embryos transferred, as assessed at PET Days 21 to 28. Mean subject implantation rate, as assessed at PET Days 21 to 28 in subjects treated with Forielle endometrial washing procedure, will be compared to the mean subject implantation rate in subjects who receive no endometrial washing (control group) following COS.

For the primary endpoint analysis addition to summary statistics, differences in mean subject implantation rate between study procedure and control procedure will be investigated and compared using Gamma/log normal regression model. The analysis model will include treatment procedure as the fixed effect and Embryo Transfer Day (Day 5 PR or Day 7 PR), age, number of follicles at baseline and number of embryos transferred per subject as covariates.

To evaluate the treatment comparison, estimated mean differences will be presented together with two-sided 95% confidence intervals and p-values. Appropriate distribution will be decided based on good ness of fit (residual sum of squares) value. This primary clinical performance endpoint analysis will be tested by planned group sequential design with O'Brien-Fleming type spending function. The study for clinical performance will be stopped at significance level of 0.003 in first (50% of subjects) interim analysis and at significance level 0.049 in final analysis.

Safety

Device incidents will be summarized using frequency and percentages for two treatment groups.

Table 1-1 Schedule of Assessments

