All subjects must have a serum β -HCG pregnancy test performed 14 days after embryo transfer (PET Day 14). Subjects may have this assessment performed by another physician; however, the pregnancy test report must be provided to the investigator. In these cases, all other PET Day 14 assessments may be performed with the subject via telephone.

If the PET Day 14 serum β -HCG pregnancy test is negative, the PET Days 21-28 and PET Days 70-84/Weeks 10-12 visits may occur by telephone with the PET Days 70-84/Weeks 10-12 visit serving as the final study contact. In these cases, the PET Days 21-28 visit and PET Days 70-84 visits may be performed via telephone and the investigator will enter negative ultrasound results for ultrasound assessments that would have been performed at PET Days 21-28 and PET Days 70-84.

Substance Code Clinical Performance and Safety Investigation of ENDOmetrial Washing
MEdical DEvice Forielle
Protocol Number MS 700623_0009

If the PET Day 14 serum β -HCG pregnancy test is positive, the subject must return to the site 21 to 28 days after embryo transfer (PET Days 21-28), to determine the number of gestational sacs present and calculate the implantation rate, the primary endpoint. The primary endpoint, the subject implantation rate, is defined as the number of intrauterine gestational sacs divided by the number of embryos transferred.

If the subject returns to the site on PET Days 21-28 for transvaginal ultrasound and does not have any gestational sacs present, the investigator will enter a negative result for the PET Days 70-84/Weeks 10-12 obstetric ultrasound (transvaginal or abdominal). In these cases, the PET Days 70-84/Weeks 10-12 final study visit may occur by telephone.

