7.1.4 Embryo Transfer Visit (Day 5 or Day 7 Post Randomization)

Subjects will return to the site 3 to 5 days after oocyte retrieval for embryo transfer. If the embryologist determines the embryos should be transferred at the cleavage stage, embryo transfer will occur on Day 5 Post Randomization. If the embryologist determines the embryos should be transferred at the blastocyst stage, embryo transfer will occur on Day 7 Post Randomization.

| | |
|------------------------|---|
| Substance Code | Clinical Performance and Safety Investigation of ENDO metrial Washing ME dicinal DE vice Forielle |
| Protocol Number | MS 700623_0009 |

The following procedures will occur at the Embryo Transfer Visit:

- Embryo transfer (maximum of 2 embryos will be transferred); if no embryos are available for transfer, the subject will exit the study and study exit procedures, as applicable, will be performed
- Provide luteal support/endometrial preparation (600 mg vaginal progesterone to be used daily from the day after Oocyte Pick Up day)
- Calculate the fertilization rate (number of zygotes divided by the number of mature (MII) oocytes inseminated)
- Record adverse events, device incidents and concomitant medications
- Schedule the Post Embryo Transfer Visit 1 (Day 14 Post Embryo Transfer)

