8.1 Sample Size

The main aim of the study is the evaluation of the clinical performance of Forielle in restoring favourable condition of endometrial milieu, after Controlled Ovarian Stimulation. For this purpose, clinical performance will be measured by assessing the difference in implantation rate in the treated arm compared to the control (standard clinical practice). Generally, the average implantation rate of ART is considered of about 25% (Nastri et al. 2013). Several works in the literature suggested the key role of endometrial receptivity on the ART outcomes (Evans et al. 2012). An improvement of about 6% in implantation rate from the usual ART outcome is clinically relevant difference. Thus, for the calculation of sample size, a clinically important difference of 6% was assumed and an interim clinical performance analysis assuming that 2 sequential tests are made using the O'Brien-Fleming spending function to determine the test boundaries. Sample sizes of 916 each arm achieve 80% power to detect a difference of 0,06 between the group proportions of 0,25 and 0,31 at a significance level (alpha) of 0,050 using a two-sided z-test with continuity correction and allocation ratio of 1:1. The total number of women to be randomised is 2,156, considering a drop-out rate of 15%.

| Target Power | Actual Power | N1 | N2 | N | P1 | P2 | Alpha |
|--------------|--------------|-----|-----|------|------|------|-------|
| 0.80 | 0.80025 | 916 | 916 | 1832 | 0.25 | 0.31 | 0.05 |

Substance Code Clinical Performance and Safety Investigation of **ENDO**metrial Washing
MEdical **DE**vice Forielle
Protocol Number MS 700623_0009

Details when Spending = O'Brien-Fleming, N1=916, N2=916, P1=0,25, P2=0,31, Continuity Correction.

| Look | Time | Lower Boundary | Upper Boundary | Nominal Alpha | Incremental Alpha | Total Alpha | Incremental Power | Total Power |
|------|------|----------------|----------------|---------------|-------------------|-------------|-------------------|-------------|
| 1 | 0.5 | -2.96259 | 2.96259 | 0.003 | 0.003 | 0.003 | 0.16425 | 0.164 |
| 2 | 1 | -1.96857 | 1.96857 | 0.049 | 0.047 | 0.047 | 0.63600 | 0.800 |

The required significance level for stopping the study for clinical performance is 0.003 to first look (50% of patients) and 0.049 at second look (final). The overall power is 80%.

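### The primary Gamma/log-normal model cannot take zeros, yet zero is the commonest implantation rate, and no rule covers zeros or women without a transfer

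*Combined protocol and SAP*

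**What the plan says.** Section 8.3.1 defines the primary endpoint as each woman's intrauterine sacs at PET Days 21–28 over her embryos transferred, and section 7.1.4 caps the embryos at two. Section 8.5.2 states that "differences in mean subject implantation rate between study procedure and control procedure will be investigated and compared using Gamma/log normal regression model"; the synopsis has the same ("compared using Gamma/log normal regression model"). The covariates are transfer day, age, baseline follicle number and number of embryos transferred. The choice between the two distributions is left open: "Appropriate distribution will be decided based on good ness of fit (residual sum of squares) value". The promised output is an estimated mean difference with a 95% confidence interval and p-value, tested at the interim and final boundaries.

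For a woman with a negative pregnancy test at PET Day 14, "the investigator will enter negative ultrasound results for ultrasound assessments" (section 5.1; sections 7.1.5 and 7.1.6 agree). At the transfer visit, "if no embryos are available for transfer, the subject will exit the study" (section 7.1.4), while "The ITT set will include all randomised subjects" (section 8.4).

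The only general fallback is in section 8.5.1: "In the case of normality assumption violations, appropriate non-parametric methods will be used for analysis". That section also defers details to separate SAPs for the interim and final analyses; these are not part of the supplied text. Section 8.1 computes power "using a two-sided z-test with continuity correction and allocation ratio of 1:1".

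**The concern.** The endpoint takes essentially three values, one of which is zero, and zero is a recorded result rather than a missing one. A log-normal model needs log(y), which does not exist at 0. A Gamma likelihood contains (shape − 1)·log(y), which is not finite at 0 unless the shape is exactly 1. The residual-sum-of-squares rule chooses between two candidates that share this defect. It states no scale for the residuals and does not say that the choice is fixed across both looks.

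To run the analysis, someone must make an unwritten choice: drop the zeros, add a constant, or solve Gamma-type mean equations without the Gamma likelihood. These choices differ in power, in the quantity estimated, or in both. Dropping zeros compares arms only among women who implanted, which conditions on the outcome.

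A woman with no embryo to transfer adds a second gap. She is in the ITT set, but her rate is 0/0, and two model covariates (transfer day and number of embryos) do not exist for her. Randomisation precedes oocyte retrieval, so such women can occur. The trial is open to investigators and subjects (section 6.10), so a confirmatory test left to be settled later is a real exposure.

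**Working it through.** **1. The plan's own figure.** For 0.25 versus 0.31, two-sided 5%, 80% power, a fixed-design z-test needs 878 per arm without continuity correction and 911 with it. With two looks at ±2.96259 and ±1.96857, 916 per arm, pooled variance and continuity correction, power is 0.8003 (stated 0.80025), and first-look power is 0.1642 (stated 0.16425). Then 1,832 / 0.85 = 2,155.3, rounded up to 2,156. The calculation reproduces, but for a test of proportions with one binary outcome per woman.

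**2. Share of exact zeros among women with a transfer.** With per-embryo rate p and within-woman correlation ρ: one embryo, P(0) = 1 − p; two embryos, P(0) = (1 − p)² + ρ·p(1 − p). The rates are from section 8.1. The single/double split and ρ are assumptions, because the documents give neither.

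| Transfers | Control | Forielle | Average |
|---|---|---|---|
| All single | 75.0% | 69.0% | 72.0% |
| Half double, ρ = 0 | 65.6% | 58.3% | 62.0% |
| All double, ρ = 0 | 56.3% | 47.6% | 51.9% |
| All double, ρ = 0.2 | 60.0% | 51.9% | 55.9% |

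That is about 951 to 1,319 zeros among 1,832 women.

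**3. The likelihoods at zero.** The log-normal log-density at 0 is −∞, as is the Gamma log-density (checked at shape 1.5). A Gamma regression fitted to data containing zeros returned a non-finite log-likelihood.

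**4. Zeros dropped.** With all double transfers and ρ = 0, the mean among positives is p / (1 − (1 − p)²) = 1 / (2 − p): 0.571 versus 0.592, a gap of 0.020 instead of 0.06. Over 50–100% double transfers and ρ from 0 to 0.4, the gap is 1.2–2.0 points. Simulated power was 11–37% (beta-binomial data, 5,000 runs per scenario, 916 per arm, final critical value 1.96857, adjusted for number of embryos where it varies). With single transfers only, every remaining value is 1 and nothing can be tested.

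**5. Zeros kept.** In the same simulation, with 0–100% double transfers, power was 82–98% for log(y + c) with c = 0.001 or 0.5, for Gamma mean equations with robust errors, for a linear model with robust (HC3) errors, and for a binomial model of sacs out of embryos with robust errors.

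The ratio reported by log(y + c) depends on c. For all double transfers and ρ = 0.2, P(0, 0.5, 1) is 0.600, 0.300, 0.100 in control and 0.51888, 0.34224, 0.13888 with Forielle. The log ratio is −0.08112·log(c) + 0.04224·log(0.5 + c) + 0.03888·log(1 + c), which gives:

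| c | 0.001 | 0.01 | 0.1 | 0.5 |
|---|---|---|---|---|
| Ratio | 1.70 | 1.41 | 1.18 | 1.07 |

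When double transfers occur, c = 0.001 and c = 0.5 disagree on significance in 1.5–2.7% of trials.

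**6. False positives (25% in both arms).** Each fixed rule rejects in about 5% of trials. Taking any significant result among zeros-kept readings gives 4.6–7.6%. Adding the positives-only reading gives about 10–12% when half or all transfers are double.

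**7. Women with no transfer, counted as 0.** With 1,078 randomised per arm and an assumed no-transfer share of 5, 10 or 15%, the 6-point difference becomes 6 × 0.95 = 5.7, 6 × 0.90 = 5.4 or 6 × 0.85 = 5.1 points. Power of an unadjusted robust linear test is 85–99%, 82–98% or 79–97% (3,000 runs per scenario).

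**The case against.** The strongest reply is that the plan does not intend zeros to be dropped. Section 8.5.2 compares mean rates in all treated and all control women, negative results are actively entered for women who are not pregnant, and the ITT set is everyone randomised. On that view, positives-only is a failure of the likelihood rather than a fair reading. The 11–37% power and most of the false-positive inflation go with it, leaving 82–98% power and at most 4.6–7.6% false positives. The separate SAPs, the independent interim statistician and the firewall further reduce the chance of a choice made after seeing results. The zero share also rests on assumed transfer numbers and correlation.

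Much of this stands. A careful statistician would probably keep the zeros, and the trial need not fail. The large power loss belongs to one reading only. The gap is shown for the supplied text; a separate SAP might fill it.

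Three things remain. First, keeping the zeros requires departing from the named likelihoods in a way that nobody has written down. A SAP would therefore have to replace the named model rather than add detail to it. Separate SAPs for the two looks do not by themselves guarantee the same rule at both. Second, the normality clause names no method and would not deliver the promised adjusted mean difference. Third, over the whole range considered, zero is the majority outcome when the arms are averaged.

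**Conclusion.** The concern holds. The named confirmatory model is unsuited to the endpoint, and the supplied text does not determine the test. Zeros make up about 52–72% of women with a transfer, averaged over arms (48–75% by arm), assuming 0–100% double transfers, correlation 0–0.4 and the protocol's own rates.

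The consequence depends on the unwritten choice. Dropping zeros leaves 11–37% power, or no test at all. Keeping them leaves adequate power, but an added constant replaces the promised mean difference with a ratio that depends on the constant. The 0/0 gap is smaller: scoring those women as 0 costs 0.3–0.9 points of effect at assumed no-transfer shares of 5–15%. It still needs a rule, because the rate and two covariates are undefined for them. This must be fixed, since the primary test cannot be run as written.

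**What to change.** In section 8.5.2 and the synopsis, remove the Gamma/log-normal model and the residual-sum-of-squares choice. Name one model that admits zeros and use it unchanged at both looks.

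- **Primary model, for example:** a linear model of the subject implantation rate with heteroscedasticity-robust standard errors, reporting the adjusted mean difference and confidence interval, with its z-statistic compared with 2.963 (interim) and 1.969 (final).
- **Sensitivity:** a binomial model of sacs out of embryos with woman-level robust errors. The two roles could be swapped, provided the choice is fixed in advance.
- **0/0 rule, for example:** count randomised women with no embryo transferred as 0 in the ITT analysis, adjusting only for age and number of follicles. Add a sensitivity analysis in women with a transfer, using all planned covariates.
- **Power:** restate it in section 8.1 for the chosen model and 0/0 rule.

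The cost is protocol and SAP wording only, with no extra data or patients, provided it is done before any unblinded look.
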